12.4. Physical Examination

The physical examination results will be displayed at each cycle. Listing of results of examinations will be provided by anatomical sites, assessment dates, and description of physical abnormalities. The number and percent of patients with abnormalities will be displayed by body system.

12.5. Vital Signs

Vital signs will be summarized at each visit for systolic blood pressure, diastolic blood pressure, pulse, respiratory rate, temperature, and weight. Actual values and change from baseline will be summarized. Listing of vital sign values will be provided.

12.6. Electrocardiogram

ECG results including ECG time, heart rate (bpm), PR interval (ms), QRS interval (ms), and QT interval (ms) (normal; abnormal, not clinically significant; abnormal, clinically significant) and comments for clinically significant abnormalities will be reported for each patient and compared to baseline. In addition, RR interval will be reported for each patient and compared to baseline and will be calculated using the following formula: $60 \text{ seconds/Heart Rate}$. QTc interval will also be calculated and reported for each patient and compared to baseline using Bazett's Formula as follows:

$$QT_C = \frac{QT}{\sqrt{RR}}$$

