Clinically significant anemia was not reported in patients dosed with 3 mg/kg or 6 mg/kg of TRC105, was reported in three of seven patients (43%; all grade 3) dosed with 8 mg/kg of TRC105, and was observed in nine of 19 (47%; three of grade 2 and six of grade 3 severity) of patients dosed with 10 mg/kg of TRC105. Anemia prompted transfusion of packed red blood cells in 10 patients and growth factors were used in five patients.

Other, less frequent, suspected adverse reactions included hypothyroidism, periorbital edema (which was generally noted prior to splitting the initial dose of TRC105), gingival pain, nausea, oral pain, vomiting, edema, decreased appetite, dyspnea, nasal congestion, rash and flushing.

Other adverse events characteristic of each individual drug were not increased in frequency or severity when the two drugs were administered together. Of note, the concurrent administration of bevacizumab and TRC105 did not potentiate the known toxicities of bevacizumab of hypertension, hemorrhage (including tumor-associated hemorrhage, and pulmonary hemorrhage or hemoptysis), or proteinuria. Reversible posterior leukoencephalopathy syndrome (RPLS), congestive heart failure, fistulae, gastrointestinal perforation impaired wound healing, and arterial thromboembolic events, were not observed.

Notably, hypertension and proteinuria, known adverse events of bevacizumab, were rarely observed when bevacizumab was given with TRC105. Mild and transient clinically significant hypertension or blood pressure increases were observed in five patients (13%; grade 3 in one case (prior to dosing with study drugs) and grade 2 in four cases) and mild transient proteinuria was observed in two patients (5%; both grade 2).

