11. **TRC105 Administration:** Intravenous TRC105 diluted in normal saline will be administered every 7 days. The first weekly TRC105 dose (cycle 1 day 1) will split into two doses whereby 3 mg/kg is administered on cycle 1 day 1 and 7 mg/kg is administered on cycle 1 day 4. The entire weekly dose of TRC105 (10 mg/kg) is then given on cycle 1 day 8 and weekly thereafter. See Section 6.1.6 for specific TRC105 administration guidelines.
12. **Axitinib Dosing:** Oral axitinib will be dosed twice daily on days 1-28 of each 28 day cycle according to the axitinib package insert. Patients who tolerate the starting dose with no adverse reactions above grade 2 for four weeks will have the axitinib dose increased. See Section 6.2 for specific dosing guidelines.
13. **Imaging:** CT or MRI scans of chest, abdomen, and pelvis with contrast to be performed at screening, and on-study as outlined in the assessment table. If subjects are unable to receive CT contrast due to CT contrast medium allergy or renal insufficiency, enhanced MRI scans may be used. A

combination of non-contrast CT and MRI studies (such as chest CT without contrast and abdominal MRI with contrast) may be used. The same method of assessment must be used throughout the course of the study thereafter. Similarly, if a subject develops a contraindication to CT contrast during the course of the study; assessments may shift to non-contrast CT of the chest and contrast-enhanced MRI of the abdomen for subsequent scans. In addition, a brain MRI or CT with contrast to be performed at screening to assure absence of CNS metastases and on study as needed if metastases are suspected. Bone scans are to be performed at screening and throughout the study at the time of CT assessments if bone metastases are present and cannot be followed by CT. Known areas of disease should be consistently followed throughout the study. Assessments should be performed whenever disease progression is suspected. Allowable window for tumor imaging studies is +/- 7 days. Scans will be performed every 56 days from date of randomization.

14. **12-Lead ECG:** Single tracing 12-lead ECG will be performed at screening and at time points indicated in the Schedule of Assessments (pre-dose). For a QTc >500 ms, a repeat ECG for confirmation and evaluation of the ECG by a cardiologist is recommended. Additional ECGs may be performed on study as clinically indicated.

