8. ASSESSMENT OF SAFETY

8.1. Safety Parameters

Safety will be characterized in terms of the incidence, timing, severity (graded by the National Cancer Institute [NCI] Common Terminology Criteria for Adverse Events [CTCAE], Version 4.0), seriousness, and relatedness of adverse events and laboratory abnormalities. In addition, physical examination, vital signs, and ECOG performance status will be serially monitored. Laboratory safety analyses will be based on the local laboratory data, and will include hematology, serum chemistry (including liver and kidney function), urinalysis, serum or urine pregnancy testing, and coagulation profile. Serum will also be assessed for immunogenicity to TRC105 (APA titers). In addition, ECGs will be recorded at baseline and day 1 of each cycle and as clinically indicated throughout the study.

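### SAP 12.6 corrects QT by Bazett alone, so a sustained heart-rate change can show as a QTc change from baseline in the descriptive ECG reporting

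*SAP*

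**What the plan says.** SAP 12.6 covers the ECG analysis. It reports "ECG results including ECG time, heart rate (bpm), PR interval (ms), QRS interval (ms), and QT interval (ms") for each patient against baseline. It adds that "RR interval will be reported for each patient and compared to baseline", with RR taken as 60 seconds divided by heart rate. On the correction it says: "QTc interval will also be calculated and reported for each patient and compared to baseline using" Bazett's formula, and prints QT over the square root of RR. No other correction appears in the SAP or the protocol.

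The protocol fixes when ECGs are taken. Section 8.1 says "ECGs will be recorded at baseline and day 1 of each cycle" and when clinically indicated. Footnote 14 to Table 10 (combination arm, weekly dosing) says "Single tracing 12-lead ECG will be performed at screening and at time points indicated in the Schedule of Assessments (pre-dose"). The table itself marks screening, day 1 of each cycle and the end-of-study visit. The same footnote gives a prompt at a QTc above 500 ms, where "a repeat ECG for confirmation and evaluation of the ECG by a cardiologist is recommended". It names no correction formula.

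For phase 2, the only ECG output in the SAP appendices is Listing 16.2.9.3.

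**The concern.** A corrected QT is meant to be free of heart rate. Bazett achieves that only if QT is proportional to RR to the power 1/2. If the true power is smaller, dividing by the square root of RR corrects too much at short RR intervals. The reported QTc then rises with heart rate and falls when the heart slows.

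This matters most when heart rate shifts between baseline and treatment, because SAP 12.6 reports change from baseline. Anemia is the obvious candidate in the combination arm. Protocol 2.3.2.1 describes it as TRC105's dose-limiting toxicity as a single agent, and 2.3.6.1 records grade 3 anemia at the recommended phase 2 dose. Anemia can persist to a pre-dose day-1 ECG, so its effect could reach the scheduled recordings. The step from anemia to a faster heart rate is physiological inference; neither document states it.

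What is at stake is how each patient's QTc change, and any informal comparison of the listings by arm, would be read. A heart-rate effect could pass for prolongation, or a slower rate could hide one.

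**Working it through.** The documents state no figure that depends on the QT formula, so there is none to reproduce. The check is algebra on the SAP's own definitions.

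**Inputs**
- From SAP 12.6: RR = 60/heart rate (seconds), and Bazett QTc = QT/RR^(1/2).
- Assumed: true QTc of 420 ms.
- Assumed: true QT–RR exponent b of 0.25 to 0.40, with 1/3 (Fridericia) as reference.
- Assumed: baseline heart rate of 70 bpm, with rises of 5 to 30 bpm.

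**Formula.** If QT = QTc0 × RR^b with QTc0 constant, then Bazett QTc = QTc0 × RR^(b − 1/2). For b < 1/2 this is above QTc0 when heart rate exceeds 60 bpm and below it when heart rate is under 60 bpm.

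**Worked case, b = 1/3.**
- At 70 bpm, RR = 60/70 = 0.857, and Bazett QTc = 420 × 0.857^(−1/6) = 430.9 ms.
- At 90 bpm, RR = 60/90 = 0.667, and Bazett QTc = 420 × 0.667^(−1/6) = 449.4 ms.
- The false change is 18.4 ms (difference taken before rounding).
- At 80 and 100 bpm the readings are 440.6 and 457.3 ms. At 50 bpm Bazett reads 12.6 ms too low.

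**False change from a 70 bpm baseline, true QTc constant at 420 ms (ms)**

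| Heart rate moves to | b = 0.40 | b = 1/3 | b = 0.25 |
|---|---|---|---|
| 75 bpm | 3.0 | 5.0 | 7.6 |
| 80 bpm | 5.7 | 9.7 | 14.8 |
| 90 bpm | 10.9 | 18.4 | 28.3 |
| 100 bpm | 15.5 | 26.4 | 40.7 |

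**Does Fridericia do better if 1/3 is not the true exponent?** Fridericia QTc = QTc0 × RR^(b − 1/3). For the same move from 70 to 90 bpm:
- b = 0.25: 420 × (1.5^(1/12) − 1.1667^(1/12)) = 434.4 − 425.4 = 9.0 ms, against 28.3 for Bazett.
- b = 0.40: 420 × (0.667^(0.0667) − 0.857^(0.0667)) = 408.8 − 415.7 = −6.9 ms, against 10.9 for Bazett.

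On the log scale, the residual heart-rate dependence is proportional to |b − 1/3| for Fridericia and |b − 1/2| for Bazett. Fridericia's is the smaller whenever b < 5/12 ≈ 0.417, which covers the whole assumed range.

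**The case against.** The strongest reply is that this is a choice between two standard formulas in a descriptive listing. The algebra shows that the formulas disagree, not which one suits these patients, and taking Fridericia as the truth would be circular. That is fair, and it is why the exponent is given as a range. The preference for Fridericia holds for exponents below about 0.417, and the documents contain nothing to confirm where these patients lie.

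A second reply is that the confounding is visible. SAP 12.6 already reports heart rate, RR and uncorrected QT against baseline, and SAP 12.5 summarises pulse at each visit. A careful reader could spot a shift and recompute. This stands as mitigation, but the QTc value the SAP commits to reporting would still move with heart rate.

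A reader might also infer more than the documents support:

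- **That infusion-reaction tachycardia will inflate QTc.** Scheduled ECGs are pre-dose, and reactions generally come with the first TRC105 dose (protocol 2.3.6.1). Only an unscheduled ECG would catch one, and SAP section 7 generally limits summary tables to planned visits. The listed signs also include bradycardia, where Bazett errs the other way.
- **That a planned between-arm QTc comparison or 500 ms count is biased.** SAP 19.3, 19.4, 20.2 and 20.3 contain neither. The 500 ms figure is a site-level prompt with no stated formula.
- **That nearly half of the combination arm will be anemic.** Protocol 2.3.2.1 says that anemia at 10 mg/kg "was observed in nine of 19 (47%; three of grade 2 and six of grade 3 severity"), but those patients received bevacizumab. For this trial's own combination, protocol 2.3.4.1 does not list anemia among the events seen, and the synopsis reports no dose-limiting toxicity at 10 mg/kg, although anemia of grade 3 or higher would have counted as one. The weekly cohorts' evaluation window was cycle 1 only, so later anemia is not excluded. The 47% still cannot be carried over.

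**Conclusion.** The concern holds in a limited form. Bazett is the only correction, and each patient's reported QTc change will follow any sustained heart-rate change if the QT–RR exponent is below 1/2. On the assumptions above, the size is about 10 ms (6 to 15) for a rise from 70 to 80 bpm and about 18 ms (11 to 28) for a rise from 70 to 90 bpm. A fall in heart rate works in the opposite direction. Whether the arms will differ in heart rate is unknown from the documents; anemia in the combination arm is a plausible route, not a demonstrated one.

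The reach is small. QTc is descriptive safety data, it is not a primary or named secondary objective, and the PFS analysis does not depend on it. This is a worthwhile improvement, not a defect that threatens a trial conclusion.

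**What to change.** In SAP 12.6, define the main QTc as Fridericia, QT/RR^(1/3) with RR = 60/heart rate in seconds, and use it for the reported change from baseline. Keep Bazett QTc as a supportive column in Listing 16.2.9.3, beside heart rate and RR, so that a reader can see when the two corrections diverge and why.

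The cost is one formula in the SAP, one derived variable in the program and one extra listing column. QT and heart rate are already captured at every scheduled ECG, so no data collection changes.

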12.7. ECOG Performance Status

The Eastern Cooperative Oncology Group (ECOG) performance grade scale will be used to measure patient ECOG performance status. The number and percent of patients in each grade category will be summarized at each visit for each dose level with individual patient data displayed in a listing.

13. Pharmacokinetic Analysis

Serum samples will be assayed to measure the concentration of TRC105 and axitinib. Only concentrations greater than or equal to the limit of qualification (LOQ) from the assay will be used. The following parameters will be determined:

- C_{\max} (ng/mL) [Maximal TRC105 concentration]
- C_{\min} (ng/mL) [Minimal TRC105 concentration]

Descriptive statistics of C_{\max} , C_{\min} , following drug administrations will be calculated by dose level and time of treatment (baseline versus patient withdrawal). Gender specific analysis will be performed if adequate data are available for each gender within a given dose cohort, e.g. the

expanded cohort at MTD. Summary PK analyses will include all patients and also include only those patients who develop positive titers for APA.

Listings of individual patient serum concentrations, actual blood sampling times, and pharmacokinetic parameters will be provided.

14. Additional Analysis

A listing of serum sample collections for anti-product antibody (APA) testing and the APA assay results will be provided. Also, the number and proportion of APA responses and changes in responses over time will be summarized. APA responses (Immunogenicity) will be measured utilizing a 3-tiered validated screening approach (screening, confirmatory, and titer) using a highly sensitive electrochemiluminescent bridging assay format.

Plasma levels of soluble angiogenic biomarkers will be listed by patient. Biomarker levels will be log-transformed before analysis, and analyses will be performed using baseline data from all available patients with continuous values for the protein analytes. PFS determined using univariate Cox proportional hazards models independent of treatment arm, and the resulting hazard ratios (HR), 95% confidence intervals (CI), and asymptotic P-values based on the score test will be reported. Multivariate Cox regression models will then test for interaction between marker level and treatment arm to identify markers predictive of benefit from axitinib or TRC105 and asymptotic P-values based on the Wald test for the interaction term will be reported. Biomarker levels will also be tested for interaction with each treatment arm separately. P-values will not be adjusted for multiple testing, and the results will be considered exploratory and hypothesis-generating. However, because high baseline levels of transforming growth factor-beta (TGF- β) receptor 3 and low baseline levels of osteopontin correlated with PFS and response rate in the Phase 1b study of TRC105 and axitinib, each of these biomarkers will be formally tested for correlation with PFS at the two-sided alpha level 0.05.

Hierarchical agglomerative clustering, using Euclidean distance and complete linkage, will be used to identify groupings among protein markers based on their baseline levels. The results will be illustrated using dendrograms. Forest plots will be created as illustrations of prognostic effect sizes (HRs and corresponding 95% CIs) with markers dichotomized as “high” or “low” relative to the median. Kaplan–Meier plots of PFS will also be created, with separate curves for each combination of treatment group by biomarker level. It has previously been shown in the Phase 1b study of axitinib and TRC105 that high baseline levels of TGF- β receptor 3 and low baseline levels of osteopontin correlated with PFS and response rate in the Phase 1b study of TRC105 and axitinib, so we will consider these biomarker levels dichotomized at the first quartile.

15. Changes from the Protocol-Specified Analysis

The details of analysis as indicated in this plan are based on the specifications of the 22Feb2016 version of the study protocol. Any later changes to the protocol may require consequential revision of this plan.

16. Programming Considerations

The format of listing and table shells should be followed as closely as possible during SAS or R programming, however, changes in format may be made due to space considerations and abbreviation of labels etc. The number of decimal places for presentation of the data should be based on the actual data, not the format presented in the shells (i.e., xx.xx is only a place holder.)

17. Appendices

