2.3.1.1. Phase 1 TRC105 Monotherapy Pharmacokinetics

In Study 105ST101, TRC105 pharmacokinetics were assessed on patients enrolled at doses up to 15 mg/kg weekly. Circulating TRC105 was not measurable above the lower limit of quantitation

of the assay (78 ng/mL) in patients receiving doses below 0.3 mg/kg. TRC105 was measurable above the target concentration based on preclinical data (200 ng/mL) for 4 hours at 0.3 mg/kg, 1 day at 1 mg/kg, 5 days at 3 mg/kg, 7 days at 10 mg/kg TRC105 dosed every two weeks. Serum concentrations expected to saturate CD105 binding sites (≥ 200 ng/mL) were achieved continuously at 15 mg/kg q2wk and 10 mg/kg weekly, and TRC105 accumulated at 15 mg/kg weekly ([Figure 1](#)).

Figure 1: Single-Dose and Multiple-Dose Pharmacokinetic Data from Study 105ST101

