- Phase 1b **cohorts 3, 4 and expanded cohort 2**: Blood sampling for TRC105 and axitinib pharmacokinetics will include a pre-infusion trough sample to be analyzed by a third party laboratory (see laboratory manual for specific instructions regarding collection times, procedures, processing, storage and shipment)
- Phase 2: Blood sampling for TRC105 and axitinib pharmacokinetics will include pre-dose trough samples to be analyzed by a third party laboratory (see laboratory manual for specific instructions regarding collection times, procedures, processing, storage and shipment).

-
- Phase 1b and Arm B of Phase 2 Only: Blood sampling for immunogenicity (APA concentrations) to be analyzed by a third party laboratory (see laboratory manual for specific instructions regarding collection, processing, storage and shipment).
 - Blood sampling for protein biomarker analysis by a third party laboratory (see laboratory manual for specific instructions regarding collection processing, storage and shipment)
 - Imaging: CT or MRI scans of chest, abdomen and pelvis in addition to any other applicable sites of disease. Scan of the chest, abdomen, and pelvis to be performed on-study as outlined in the assessment table. Known areas of disease should be consistently followed throughout the study. Bone scans are to be performed at screening and throughout the study at the time of CT assessments if bone metastases are present and cannot be followed by CT. Brain MRI or CT with contrast to be performed at screening to assure absence of CNS metastases and on study as needed if metastases are suspected.
 - **For phase 1b:** scans will be performed on day 22 of cycle 2, 4, and 6. Beyond cycle 6 scans will be performed every 3 cycles (Day 22 of cycle 9, 12, 15, etc.).
 - **For Phase 1b Cohort 3, 4 and Expanded Cohort 2:** scans will be performed on every 56 days from cycle 1 day 1.
 - **For phase 2:** scans will be performed every 56 days from date of randomization. Assessments should be performed whenever disease progression is suspected. Allowable window for tumor imaging studies is +/- 7 days.
 - Administration of TRC105. TRC105 diluted in normal saline will be administered as a 1 to 4 hour infusion (+/- 15 minutes) following premedication (see [Section 6.1.6](#)) according to the pertinent schedule of assessment.

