A hazard ratio (HR) of 0.67 is considered to be clinically relevant. Based on 1:1 randomization and the use of a one-sided log-rank test at the $\alpha=0.10$ level of significance, 115 events are required in order to have 80% power to detect a HR of 0.67. The expected PFS of patients treated with axitinib who have progressed following first line treatment with a VEGFR TKI is 4.8 months. Based on a planned accrual period of 12 months, and a minimum follow-up period of 4.3 months, approximately 150 patients will be required. Timing of the final analysis of PFS will be determined by the sponsor based on the expected total number of events that define PFS and the timing of these events, and may occur prior to the occurrence of 115 events.

5. Analysis Population

The safety population includes all patients who receive at least a portion of one dose of the study drug, TRC105 or axitinib (phase 2 portion).

The phase 2 study population for efficacy will include all randomized patients (intention to treat).

The Phase 1b study population for efficacy will include all patients who receive treatment with axitinib and TRC105.

6. General Analysis Comments

Summary statistics will include frequencies and percents of responses in each category for discrete measures; and may include means, medians, standard deviations, minimum and maximum values for continuous measures. Listings of data represented on the Case Report Form (CRF) will be provided.

SAS[®], Version 9.0 or higher or R version 2.15 or higher, will be used to perform all statistical analyses.

7. Missing Data

All data collected, including unscheduled visits, will be presented in the data listings. Summary tables will generally be limited to planned visits.

In all analyses, except for partial dates, it is expected that only observed values will be presented; no imputation of missing data will be conducted. Partial dates will be imputed according to the following table. CRFs that are not listed below are not expected to contain partial dates. CRF versions may change. Only if a change impacts the imputation of a partial date will the SAP be amended.

Planned Imputation Methods for Partial Dates

CRF	Field	Planned Imputation Method	
		Month and Year Given	Year Given
Adverse Events	Date of Onset	First of Month	Jan 01 of Year
	Date of Resolution	Last day of Month	Dec 31 of Year
Concomitant Medications	Start Date	First of Month	Jan 01 of Year
	Stop Date	Last day of Month	Dec 31 of Year

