14.3.4.3. Clinical Laboratory Results – Chemistry: Change from Baseline

14.3.4.4. Clinical Laboratory Results – Urinalysis: Change from Baseline

19.3. Tables in Text Phase 2 (by treatment group) :

- Protocol Versions under which Each Patient was Treated

Enrollment by country by Treatment Group

- Disposition of Patients by Treatment Group
- Incidence of Protocol Deviations by Treatment Group
- Demographics and Baseline Characteristics
- Screening ECOG Performance Status
- Past Cancer Treatment
- Primary Cancer Diagnoses by Treatment Group
- Disease Present at Screening
- Best Overall Response and Duration of Response
- Summary of Serum TRC105 Pharmacokinetic Parameters Following Multiple Intravenous Infusions of TRC105
- Most Common ($n > 1$) and all Grade 3 and 4 Adverse Events by System Organ Class, by Preferred Term and by Grade
- Most Common ($N > 1$) and all Drug-Related Grade 3 and 4 Adverse Events by System Organ Class, by Preferred Term and by Graded Full Analysis Population
- Anti-Product Antibody (APA)
- PFS by Central Review
- PFS by Investigator Assessment

Cox proportional hazard model of PFS

19.4. Appended Tables Phase 2 (by arm):

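### SAP Section 13 deletes concentrations below the LOQ, which can only push the trough summaries upward, and does not limit Cmax to the cohorts that have peak samples

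*SAP*

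**What the plan says.** SAP Section 13 sets the rule for TRC105 and axitinib concentrations: "Only concentrations greater than or equal to the limit of qualification (LOQ) from the assay will be used". SAP Section 7 adds that, partial dates apart, "no imputation of missing data will be conducted". Neither section asks for the number of samples below LOQ.

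Section 13 names two parameters, Cmax ("Maximal TRC105 concentration") and Cmin ("Minimal TRC105 concentration"), with no limit to a phase or cohort. Their descriptive statistics "will be calculated by dose level and time of treatment (baseline versus patient withdrawal"), and a separate summary is planned for patients with positive anti-product antibody (APA) titers. SAP Section 19.3 lists among the Phase 2 in-text tables a "Summary of Serum TRC105 Pharmacokinetic Parameters Following Multiple Intravenous Infusions of TRC105".

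On sampling, Protocol Section 4.1.2.2 draws a trough and an end-of-infusion peak in Phase 1b cohorts -1, 1, 2 and Expanded Cohort 1. Cohorts 3, 4 and Expanded Cohort 2 have a trough only. For Phase 2 the text is: "Phase 2: Blood sampling for TRC105 and axitinib pharmacokinetics will include pre-dose trough samples". Protocol Section 9.1.1.1 heads peak sampling as Phase 1b, and Protocol Section 10.4 ties pharmacokinetic parameters to Phase 1b.

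**The concern.** A value below LOQ is informative: it says that the concentration was low. Removing it cuts off the lower tail and summarises the rest as if it were the whole. A patient whose lowest sample is below LOQ either drops out of the Cmin summary or enters it with the next-lowest quantifiable value.

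The samples most likely to be lost are in groups that the trial samples or reports:

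- **Withdrawal and follow-up.** Tables 10 and 11 take samples at end of study and 28 days later. In Arm B the end-of-study visit is timed from the last dose of TRC105 or axitinib, and Protocol Section 5.2 lets some patients continue on axitinib alone, so that sample may come long after the last infusion.
- **Reduced every-two-week doses**, which Protocol Table 15 allows.
- **APA-positive patients.** If antibodies lower exposure, deletion would mask it.
- **Baseline.** Phase 2 excludes prior TRC105, so Cycle 1 Day 1 pre-dose samples should be below LOQ, and the baseline column would be empty or nearly so.

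Separately, where only troughs are drawn, a reported Cmax would be the largest trough.

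**Working it through.** The plan states no figure here to reproduce. The check has a text part and an illustrative calculation.

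**1. Parameters against sampling**

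| Group | End-of-infusion peak drawn? | Cmax estimable? |
|---|---|---|
| Phase 1b cohorts -1, 1, 2, Expanded Cohort 1 | Yes (Protocol 4.1.2.2, Table 7) | Yes |
| Phase 1b cohorts 3, 4, Expanded Cohort 2 | No (Protocol 4.1.2.2, Table 8) | No |
| Phase 2 Arm B | No (Protocol 4.1.2.2, Tables 10 and 11) | No |

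**2. Direction of the bias**

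Removing every value below a fixed limit cannot lower the mean or the median of what remains. The bias is zero only if no sample is below LOQ.

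**3. Where below-LOQ values are likely**

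Protocol Section 2.3.1.1 reports, for the earlier monotherapy study, an assay limit of 78 ng/mL and a target of 200 ng/mL. At 10 mg/kg weekly and 15 mg/kg every two weeks, levels stayed at or above target throughout. At doses given every two weeks, time above target was "for 4 hours at 0.3 mg/kg, 1 day at 1 mg/kg, 5 days at 3 mg/kg, 7 days at 10 mg/kg". This trial's own LOQ is not stated.

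**4. Size under stated assumptions**

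Assume lognormal troughs with log-SD s, a fraction p of them below LOQ, and a = z(p), the standard normal quantile. Then, for retained values relative to all values:

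- mean ratio = Φ(s − a) / (1 − p)
- median ratio = exp(s · z((1 + p)/2))

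Example with p = 0.10 and s = 1.0: a = −1.2816. The mean ratio is Φ(2.2816)/0.90 = 0.9887/0.90 = 1.099. The median ratio is exp(1.0 × 0.1257) = 1.134.

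| p (assumed) | Mean, s = 0.5 | Mean, s = 1.0 | Median, s = 0.5 | Median, s = 1.0 |
|---|---|---|---|---|
| 2% | +1.5% | +1.9% | +1.3% | +2.5% |
| 5% | +3.6% | +4.8% | +3.2% | +6.5% |
| 10% | +7.0% | +9.9% | +6.5% | +13.4% |
| 20% | +13.8% | +20.9% | +13.5% | +28.8% |
| 30% | +21.0% | +33.8% | +21.3% | +47.0% |

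**5. Are those fractions plausible?**

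Under the same model the true median trough is LOQ × exp(−s · a). With LOQ = 78 ng/mL and p = 10%, 20% and 30%, it is 148, 119 and 101 ng/mL for s = 0.5, and 281, 181 and 132 ng/mL for s = 1.0. All but one of these lie below 200 ng/mL. The 10% to 30% rows therefore do not describe full-dose troughs that stay above 200 ng/mL; for those, the 2% row or less is the better guide. The lower rows are relevant only to the groups named under the concern.

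**The case against.** The case against has real force.

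- **Full-dose exposure was adequate before.** Levels were continuously at or above 200 ng/mL at two of the regimens used here, and Protocol Section 2.3.2.1 reports the same for 10 mg/kg with bevacizumab. This stands, and it is why the bias at full dose is probably small.
- **Time above target is not time above LOQ.** A reader might infer from the 7-day figure at 10 mg/kg every two weeks that many troughs will be below LOQ. The documents do not show that: the figure refers to 200 ng/mL, not 78, and in this trial that dose arises only as a reduction step in Table 15.
- **Deletion does not leave only well-exposed patients.** That inference also fails. Values between 78 and 200 ng/mL are below target, yet they would be kept.
- **The objective is modest.** It is to characterise the pharmacokinetic profile; no above-target endpoint is planned.
- **The data are not lost.** Individual concentrations are listed, and Protocol Section 9.1.1.1 plans a population analysis of TRC105. True, but neither corrects the Section 13 summaries.
- **A Phase 2 Cmax is not named outright.** Section 13 speaks of dose levels and the expanded cohort, and the Section 19.3 title could be met by Cmin alone. That the SAP plans a Phase 2 Cmax is an inference from unrestricted wording together with that table. What stands is that nothing in the SAP prevents it.
- **The baseline gap loses no exposure information**, since those patients have not yet had the drug. It is a defect in the time-point definition.

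**Conclusion.** The concern holds in a limited form. Section 13 sets a deletion rule, and that rule biases the descriptive Cmin summaries upward whenever any trough is below LOQ. The direction is certain; the size is unknown. It is probably small for full-dose on-treatment troughs. For late samples, reduced every-two-week doses and APA-positive patients it could reach 7% to 34% for the mean and 6% to 47% for the median, if 10% to 30% of samples were below LOQ and troughs were lognormal with log-SD 0.5 to 1.0. Those fractions and that spread are assumptions, and the 78 ng/mL limit comes from another study.

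The unrestricted Cmax is a plain mismatch with the sampling schedule for Phase 2 and for Phase 1b cohorts 3, 4 and Expanded Cohort 2. Both points concern a secondary, descriptive analysis. The primary PFS comparison is untouched.

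**What to change.** Amend SAP Section 13 and the Section 19.3 table as follows:

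1. Keep below-LOQ samples in the denominator and report their number and percent at each time point.
2. Give medians and quartiles with below-LOQ values ranked lowest, showing the statistic as below LOQ where it falls there. Ranking is not imputation, so Section 7 can stand. Substituting half the LOQ is one convention among several and would need an exception to Section 7.
3. For TRC105, add the percent of samples at or above 200 ng/mL.
4. Exclude pre-first-dose samples from Cmin; otherwise the minimum would be below LOQ for every TRC105-naive patient who has such a sample.
5. Restrict Cmax to Phase 1b cohorts -1, 1, 2 and Expanded Cohort 1. Report trough only elsewhere, including the Phase 2 table.

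The cost is a few lines of SAP text and slightly more reporting, with no new sampling. Troughs may look less favourable.
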